### 8.5 Toxicity/ Symptoms

- AEs, no.events (%) by treatment arm, no. patients(%) by treatment arm, Risk ratio with 95% CI
  - ARs, no.events (%) by treatment arm, no. patients(%) by treatment arm, Risk ratio with 95% CI
  - SAEs, no. events (%) by treatment arm, no. patients (%) by treatment arm, Risk ratio with 95% CI
  - SARs, no. events (%) by treatment arm, no. patients (%) by treatment arm, Risk ratio with 95% CI
  - UARs, no. events (%) by treatment arm, no. patients (%) by treatment arm, Risk ratio with 95% CI
  - SUSARs, no. events (%) by treatment arm, no. patients (%) by treatment arm, Risk ratio with 95% CI
  - Fatal AEs/SAEs, no. events (%) by treatment arm, no. patients (%) by treatment arm, Risk ratio with 95% CI
  - Safety bloods, mean(SD) by treatment arm at baseline and week 8
- AEs, ARs, SAEs, SARs, UARs and SUSARs will also be presented by system organ class.

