### 10.1.5 Follow Up (Week 12 +/- 7 days) Procedures

For those patients who withdraw from the trial / discontinue the study drug prior to 8 weeks or following the completion of 8 weeks of treatment, the CI or designee will contact the patient by telephone 4 weeks post study drug termination to assess if the patient is experiencing any adverse events. Participants will be asked regarding exacerbation status and if applicable exacerbations will be documented.

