### **12.7 Adverse Event Reporting Period**

The AE reporting period for this trial begins on enrolment into the trial and ends 28 days following the administration of the study drug. All AEs assessed as possibly, probably or definitely related to the study drug and all SAEs that occur during this time will be followed until they are resolved or are clearly determined to be due to a patient's stable or chronic condition or intercurrent illness(es).

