## **13 STATISTICAL CONSIDERATIONS**

### 13.1 Sample Size

A sample size of 31 subjects per group will have 90% power at a two-tailed significance level of 0.05 to detect a difference in the primary efficacy outcome EBV shedding of 70% in the treated group to 30% in the control group. With a dropout rate of approximately 30%, this study will require a total of 44 patients per group.

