### 8.3 Trial treatment

- Number of patients receiving at least one unit/dose of the drug, n(%) by treatment arm
- Duration of study drug (days), mean(SD) by treatment arm
- Overall compliance, mean(SD) by treatment arm
- Compliance, n(%) by treatment arm
- Time lapse between randomisation and study drug administration, mean(SD) by treatment arm
- Reason for study drug termination, n(%) by treatment arm
- Protocol Deviations/Violations, n(%) by treatment arm
- Premature withdrawals, n(%) by treatment arm

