**Table x.x: Safety Outcomes**

	Number of Events			Number of Patients				p-value
	Total (n=)	Valaciclovir (n=)	Placebo (n=)	Total (n=)	Valaciclovir (n=)	Placebo (n=)	RR (95%I)	
Adverse Events	n (%)	n (%)	n (%)	n (%)	n (%)	n (%)	x.x (x.x to x.x)	x.xx
Adverse Reactions	n (%)	n (%)	n (%)	n (%)	n (%)	n (%)	x.x (x.x to x.x)	x.xx
Unexpected Adverse Reactions	n (%)	n (%)	n (%)	n (%)	n (%)	n (%)	x.x (x.x to x.x)	x.xx
Serious Adverse Events	n (%)	n (%)	n (%)	n (%)	n (%)	n (%)	x.x (x.x to x.x)	x.xx
Serious Adverse Reactions *	n (%)	n (%)	n (%)	n (%)	n (%)	n (%)	x.x (x.x to x.x)	x.xx
Suspected Unexpected Serious Adverse Reactions	n (%)	n (%)	n (%)	n (%)	n (%)	n (%)	x.x (x.x to x.x)	x.xx
Fatal Serious Adverse Events	n (%)	n (%)	n (%)	n (%)	n (%)	n (%)	x.x (x.x to x.x)	x.xx

\*Primary safety outcome (incidence of serious adverse reactions)

AEs, ARs, SAEs, SARs, UARs and SUSARs will also be presented by system organ class.

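### Adverse-event collection after early stopping is not settled, and the crude safety comparison would be modestly biased if the time observed differed by arm

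*SAP*

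**What the plan says.** **Window.** Protocol 12.7 says the adverse-event reporting period "ends 28 days following the administration of the study drug". It does not say which administration is meant. The parallel pregnancy window in Protocol 12.11 does name the final dose. Protocol 10.1.5 describes the last safety contact. It covers "For those patients who withdraw from the trial / discontinue the study drug prior to 8 weeks or following the completion of 8 weeks of treatment", and the investigator or designee "will contact the patient by telephone 4 weeks post study drug termination". The heading of that section nevertheless places the contact at week 12.

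**Text pointing to a common 12 weeks.** Protocol 5.7 ends the trial once participants have completed 12 weeks of follow-up. Protocol 7.3 keeps patients who ask to stop drug in follow-up. Protocol 12.2 has adverse events asked about at every visit once treatment has begun. Table 2 marks adverse events at visit 1 and at weeks 4, 8 and 12.

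**Analysis.** SAP 7.1 compares SARs by Fisher's exact test with a relative risk. SAP 8.5 lists AEs, ARs, SAEs, SARs, UARs, SUSARs and fatal events in one format, as in "SAEs, no. events (%) by treatment arm, no. patients (%) by treatment arm, Risk ratio with 95% CI". The Safety Outcomes table in SAP Appendix 1 follows it and flags the SAR row: "Primary safety outcome (incidence of serious adverse reactions)". SAP 8.3 summarises "Duration of study drug (days), mean(SD) by treatment arm", but that duration plays no part in the safety comparison.

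**The concern.** A patient-level risk ratio is a fair comparison when both arms are watched for the same length of time. If observation ends 28 days after a patient's own stop, its length depends on stopping, which treatment can affect. An arm with more early stopping then has less time in which unrelated illness, admissions and deaths can be recorded, and its crude percentages fall for that reason alone. If that arm were valaciclovir, the error would favour a conclusion of safety, and safety is one of the two primary objectives (Protocol 4.3).

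The event columns have a further weakness. A percentage of events has no stated denominator, although events can recur within a patient, and event counts receive no between-arm estimate.

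**Working it through.** **What the documents supply.** Treatment lasts 8 weeks (Protocol 9.1), so a completer's window is 56 + 28 = 84 days. There are 44 patients per arm (Protocol 13.1; 31/0.70 = 44.3). The documents give no observation time, event risk or early-stopping fraction by arm, so there is no planned figure to reproduce on this point.

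**The sections set against one case.** Take a patient who stops at day 14.
- Under Protocol 12.7 and 10.1.5, read as patient-specific, the window closes at day 14 + 28 = 42, half of 84 days.
- Under Protocol 7.3, 12.2 and Table 2, the same patient is still asked about adverse events at weeks 8 and 12.
- An SAE in week 7 falls outside the first window and inside the second. Neither document says whether it is counted.

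**Size if the patient-specific window applies.** Assumptions (not in the documents): constant hazard; stopping independent of events; a fraction f stops early, all at day s; 12-week risk p = 10%; f = 10% on placebo and 20%, 30% or 40% on valaciclovir; no true difference.

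Crude risk in an arm = (1 − f)·p + f·[1 − (1 − p)^((s + 28)/84)].

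Central case, 30% v 10% stopping at day 14:
- Risk over 42 days = 1 − 0.9^0.5 = 0.0513.
- Valaciclovir: 0.7 × 0.10 + 0.3 × 0.0513 = 0.0854.
- Placebo: 0.9 × 0.10 + 0.1 × 0.0513 = 0.0951.
- Crude risk ratio = 0.90, where the truth is 1.00.
- Mean observation: 0.7 × 84 + 0.3 × 42 = 71.4 days v 0.9 × 84 + 0.1 × 42 = 79.8 days. The ratio of 0.895 is also the expected ratio of event counts.

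| Early stopping, valaciclovir v placebo | Null RR, stop at week 2 | Null RR, stop at week 4 |
|---|---|---|
| 10% v 10% | 1.00 | 1.00 |
| 20% v 10% | 0.95 | 0.97 |
| 30% v 10% | 0.90 | 0.93 |
| 40% v 10% | 0.85 | 0.90 |

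Widening the assumptions to stops between day 7 and day 42 and risks of 5% to 60%, with the same stopping fractions, gives 0.82 to 0.99. With a true hazard ratio of 1.5 in the central case, the crude ratio falls from 1.46 (everyone followed for 84 days) to 1.32.

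**Random error for scale.** With 44 per arm and 10% risk in each, SE(log RR) = √(2 × 0.9/(44 × 0.1)) = 0.64. The 95% interval around a null ratio is then exp(±1.96 × 0.64), about 0.29 to 3.50.

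**When the adverse event itself causes stopping.** Assume a 60% 12-week AE risk. On placebo 10% stop at week 2 for unrelated reasons. On valaciclovir 30% stop at week 2, of which 20 points stop because of an AE. Risk over six weeks = 1 − 0.4^0.5 = 0.3675.
- Valaciclovir: 0.20 + 0.10 × 0.3675 + 0.70 × 0.60 = 0.6568.
- Placebo: 0.90 × 0.60 + 0.10 × 0.3675 = 0.5768.
- Crude ratio = 1.139. With full follow-up it is (0.20 + 0.80 × 0.60)/0.60 = 1.133.

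The patient-level AE row is essentially unbiased here, because the event that led to stopping is already counted.

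**The case against.** A reader might infer that the plan fixes the end of collection at each patient's last dose. It does not say so. Protocol 12.7 omits the word last, and Protocol 5.7, 7.3, 12.2 and Table 2 support a shared 12-week window, under which the bias does not arise. This stands. The patient-specific window is the more natural reading of 12.7 with 10.1.5, but it remains a reading.

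A reader might also infer that valaciclovir will look falsely safe whenever it is poorly tolerated. The documents do not support that either. The 30% dropout in Protocol 13.1 is overall, is not split by arm, and is not the same as stopping drug. Patients who stop because of an adverse event are already in the patient count. SAP 8.3 and its table show duration of drug, reasons for termination and withdrawals by arm, so unequal stopping would be visible. Visibility does not correct the estimates, however.

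The third inference would be that the primary safety outcome is biased. SARs are judged drug-related, and treatment plus 28 days is a defensible risk period for such events. No distortion of that comparison has been shown.

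Person-time rates are not a complete remedy. Suppose a true rate ratio of 1.3 acts only while on drug, with 30% v 10% stopping at week 2. The rate ratio is then [0.7 × (8 × 1.3 + 4) + 0.3 × (2 × 1.3 + 4)]/10.2 = 12.06/10.2 = 1.18. A rate also treats stopping as uninformative. This limits rates to a supporting role.

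**Conclusion.** The point holds in a conditional and modest form. The sections on adverse-event collection after early stopping conflict and must be reconciled. The planned comparison makes no allowance for time observed. If the patient-specific window is the operative one and early stopping differs by arm, all-cause SAEs, deaths and event counts are understated in the arm that stops earlier. In the assumed scenarios a null risk ratio reads about 0.85 to 0.97 at a 10% 12-week risk, which is small against the random error with 44 per arm. The bias is absent when stopping is equal, close to nil for the AE patient count when the AE causes the stop, and not shown for SARs. The stopping fractions, stop times, event risk and constant hazard are all assumptions. It is still worth correcting, because the possible error runs in a known direction and the correction is cheap.

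**What to change.** 1. Reconcile Protocol 12.7, 10.1.5, 7.3, 12.2, 5.7 and Table 2, so that one statement says how long adverse events are collected after early stopping and which events enter the analysis.
2. In SAP 8.5, compare SAEs and deaths over a common 12-week window in all randomised patients, using the planned contacts and the online health-record review already described in the protocol's Study Procedures Amendment Summary.
3. Report adverse-event observation time by arm, with its start and end defined in the SAP.
4. In SAP 8.5 and the Safety Outcomes table, replace the percentage of events with the number of events and events per unit of person-time. Add a rate ratio with 95% CI, labelled supportive.
5. Keep patients n (%), the risk ratio, and Fisher's exact test for SARs as planned.

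The cost is clarifying wording in the protocol, a few lines in the SAP and some extra table columns. The drug start date is already recorded (Protocol 10.2.6) and duration of drug is already derived (SAP 8.3). For patients who withdraw consent, the common window depends on the permission to use medical records that Protocol 7.3 says will be sought, so some gaps may remain. The rates assume a roughly constant hazard and uninformative stopping, which is why they sit beside the crude figures and do not replace them.

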## 9. ADDITIONAL INFORMATION

### 9.1 Data Monitoring and Ethics Committee (DMEC)

A DMEC will be appointed with responsibility for safeguarding the interests of trial patients, they will monitor the main outcome measures including safety and efficacy so as to protect the validity and credibility of the trial. The committee members will be independent of the study team and will comprise of at least two respiratory specialists and one statistician. The DMEC Charter will outline the terms of reference of the DMEC including roles/responsibilities, membership, organisation of meetings, reporting, decision-making and the relationship with the other trial committees.

The DMEC will discuss trial progress as and when required, but at least every 9 months, meetings will be held and will be formally minuted. The Trial Statistician will produce reports for the DMEC including recruitment, baseline, adverse event, compliance and outcome data to enable them to monitor the trial and guide overall progress. An interim analysis of efficacy is not planned, although this can be requested by the DMEC as required.

The DMEC will function primarily as a check for safety reviewing adverse events (AEs). They will specifically review the incidence of ARs, SAEs and SUSARs and produce a recommendation following each meeting. They will report any issues pertaining to safety to both the study sponsor and the Chief Investigator. If concerns exist about participant safety it will be the responsibility of both to take appropriate action to halt the trial immediately.

**APPENDIX 1: EXAMPLE DRAFT SUMMARY TABLES, FIGURES AND LISTINGS**

**Figure A1. The CONSORT Diagram**

**Table x.x: Reason for Exclusion From the Study**

Total number of patients screened		n
Total number of patients recruited		n
Total number of patients excluded		n
Reasons for Exclusion	The patient is not over 18 years of age?	n
	The patient does not have a clinical diagnosis of COPD	n
	The patient does not display the presence of Epstein-Barr virus on sputum PCR analysis?	n
	Respiratory failure (defined as long-term oxygen therapy).	n
	An acute exacerbation of COPD in the previous month	n
	A diagnosis of asthma.	n
	Patient has known hypersensitivity to valaciclovir or aciclovir.	n
	Patient unable to swallow study drug capsules.	n
	Established diffuse interstitial lung disease (e.g. Idiopathic Pulmonary Fibrosis).	n
	Established diagnosis of symptomatic bronchiectasis.	n
	Patient known to be pregnant or breastfeeding.	n
	Patient has an estimated creatinine clearance less than 50ml/minute.	n
	Patient is known to have participated in investigational medicinal product trials within 30 days.	n
	Patient does not adequately understand verbal or written information.	n
	Concomitant use of nephrotoxic medicinal products or medicines associated with altered renal tubular secretion.	n
Other	n	

Table x.x: Baseline Characteristics at Trial Entry

Baseline Characteristics		Treatment Group		Total
		Valaciclovir	Placebo	
		N	n	
Gender	Male	n (%)	n (%)	n (%)
	Female	n (%)	n (%)	n (%)
Age (years)		xx.x (xx.x)	xx.x (xx.x)	xx.x (xx.x)
Height(m)		xx.x (xx.x)	xx.x (xx.x)	xx.x (xx.x)
Weight(kg)		xx.x (xx.x)	xx.x (xx.x)	xx.x (xx.x)
BMI(kg/m2)		xx.x (xx.x)	xx.x (xx.x)	xx.x (xx.x)
Transfer Factor((TLCO) as a percentage of the predicted value(%))		xx.x (xx.x)	xx.x (xx.x)	xx.x (xx.x)
Forced Expiratory Volume(FEV1 (L))		xx.x (xx.x)	xx.x (xx.x)	xx.x (xx.x)
Forced Vital Capacity(FVC (L))		xx.x (xx.x)	xx.x (xx.x)	xx.x (xx.x)
FEV1/FVC Ratio (%) ,		xx.x (xx.x)	xx.x (xx.x)	xx.x (xx.x)
Mid Expiratory Flow (MMEF 25-75% (L/s))		xx.x (xx.x)	xx.x (xx.x)	xx.x (xx.x)
Peak Expiratory Flow(PEF (L/s)),		xx.x (xx.x)	xx.x (xx.x)	xx.x (xx.x)
Smoking Status	Current Smoker	n (%)	n (%)	n (%)
	Ex-Smoker	n (%)	n (%)	n (%)
	Never Smoked	n (%)	n (%)	n (%)
Pack years		xx.x (xx.x)	xx.x (xx.x)	xx.x (xx.x)
Presence of EBV	Yes	n (%)	n (%)	n (%)
	No	n (%)	n (%)	n (%)
Quantitative PCR Titre(copies)		xx.x (xx.x)	xx.x (xx.x)	xx.x (xx.x)

Relevant co-morbidities		n (%)	n (%)	n (%)
Pre-existing Cardiovascular issues		n (%)	n (%)	n (%)
Any exacerbations in past 12 months	Yes	n (%)	n (%)	n (%)
	No	n (%)	n (%)	n (%)
If Yes, Number of exacerbations in past 12 months		x.x (x.x to x.x)	x.x (x.x to x.x)	x.x (x.x to x.x)
If Yes, Number of exacerbations in past 12 months requiring steroids		x.x (x.x to x.x)	x.x (x.x to x.x)	x.x (x.x to x.x)
If Yes, Number of exacerbations in past 12 months requiring antibiotics		x.x (x.x to x.x)	x.x (x.x to x.x)	x.x (x.x to x.x)
If Yes, Number of exacerbations in past 12 months resulting in hospitalization		x.x (x.x to x.x)	x.x (x.x to x.x)	x.x (x.x to x.x)

Mean (SD) (or median (IQR)) presented for continuous variables and no. (%) for all categorical variables.

Table x.x: Treatment after Trial Entry Treatment Termination, Protocol Deviation

		Valaciclovir N = <n>	Placebo N = <n>
Number of patients who received at least one dose of treatment		n (xx.x%)	n (xx.x%)
Duration of study drug (days)		xx.x (x.x)	xx.x (x.x)
Overall compliance		xx.x (x.x)	xx.x (x.x)
Compliance	≥80%	n (xx.x%)	n (xx.x%)
	60-79%	n (xx.x%)	n (xx.x%)
	<60%	n (xx.x%)	n (xx.x%)
Time from randomisation to start of study drug (hours)		xx.x (xx.x to xx.x)	xx.x (xx.x to xx.x)
Reasons for termination of study drug			
1) Study Drug related AE		n (xx.x%)	n (xx.x%)
2) Study Drug related SAE		n (xx.x%)	n (xx.x%)
3) Study Drug Expiry Date		n (xx.x%)	n (xx.x%)
4) Patient Request		n (xx.x%)	n (xx.x%)
5) Clinician's Request		n (xx.x%)	n (xx.x%)
6) Other		n (xx.x%)	n (xx.x%)
Protocol deviations/ violations			
Eligibility		n (xx.x%)	n (xx.x%)
Consent		n (xx.x%)	n (xx.x%)
Study Drug Administration			
Did not receive allocated treatment a		n (xx.x%)	n (xx.x%)
Received treatment of other group b		n (xx.x%)	n (xx.x%)
Study drug omitted in error c		n (xx.x%)	n (xx.x%)
Study drug received in error		n (xx.x%)	n (xx.x%)
SAE reporting timelines		n (xx.x%)	n (xx.x%)
Visit outside schedule		n (xx.x%)	n (xx.x%)
Other		n (xx.x%)	n (xx.x%)
Premature Withdrawals			
Adverse Event		n (xx.x%)	n (xx.x%)
Serious Adverse Event		n (xx.x%)	n (xx.x%)
Protocol deviation/ non-compliance		n (xx.x%)	n (xx.x%)
Lost to Follow Up		n (xx.x%)	n (xx.x%)
Withdrawal of patient consent		n (xx.x%)	n (xx.x%)
Death		n (xx.x%)	n (xx.x%)
At clinician's request		n (xx.x%)	n (xx.x%)
Other		n (xx.x%)	n (xx.x%)

a-Numbers based on study drug administration data, b- Numbers based on the randomisation listing held by trial Statistician, c- Numbers based on Protocol deviation data

**Table x.x: Primary Efficacy Outcome Analyses**

		Valaciclovir N = <n>	Placebo N = <n>	Difference (95% CI)	p-value
Number of patients experiencing suppression of Epstein-Barr virus in the sputum of subjects with COPD will be assessed using quantitative PCR at baseline and 8 weeks.*	Intention to Treat#	N(%)	N(%)	xx.x (xx.x – xx.x)	0.xx
	Per Protocol	N(%)	N(%)	xx.x (xx.x – xx.x)	0.xx
Change in viral load from baseline to week 8	Intention to Treat	xx.x(xx.x)	xx.x(xx.x)	xx.x (xx.x – xx.x)	0.xx
Change in viral load from baseline to week 8	Per Protocol	xx.x(xx.x)	xx.x(xx.x)	xx.x (xx.x – xx.x)	0.xx

\*Odds Ratio and 95% Confidence Interval Presented

#Primary Analysis

**Table x.x: Primary Efficacy Outcome Subgroup**

EBV Supression (Yes)		Valaciclovir N = <n>	Placebo N = <n>	OR (99% CI)
Overall Compliance	≥80%	N(%)	N(%)	x.xx (xx.x – xx.x)
	60-79%	N(%)	N(%)	x.xx (xx.x – xx.x)
	<60%	N(%)	N(%)	x.xx (xx.x – xx.x)

*Odds Ratio and 99% CI from the treatment\*subgroup interaction models are presented*

Table x.x: Lung Function/ Sputum Sample Descriptive Statistics

	Valaciclovir			Placebo		
	Baseline	Week 4	Week 8	Baseline	Week 4	Week 8
	n=<n>	n=<n>	n=<n>	n=<n>	n=<n>	n=<n>
Lung Function						
Forced Expiratory Volume (FEV1 (L))	xx.x (x.x)	xx.x (x.x)	xx.x (x.x)	xx.x (x.x)	xx.x (x.x)	xx.x (x.x)
Forced Expiratory Volume in 1 second (FEV1 as a percentage of the predicted FEV1 value (%))	xx.x (x.x)	xx.x (x.x)	xx.x (x.x)	xx.x (x.x)	xx.x (x.x)	xx.x (x.x)
Forced Vital Capacity (FVC (L))	xx.x (x.x)	xx.x (x.x)	xx.x (x.x)	xx.x (x.x)	xx.x (x.x)	xx.x (x.x)
FEV1/FVC Ratio (%)	xx.x (x.x)	xx.x (x.x)	xx.x (x.x)	xx.x (x.x)	xx.x (x.x)	xx.x (x.x)
Mid Expiratory Flow (MMEF 25-75% (L/s))	xx.x (x.x)	xx.x (x.x)	xx.x (x.x)	xx.x (x.x)	xx.x (x.x)	xx.x (x.x)
Peak Expiratory Flow(PEF (L/s))	xx.x (x.x)	xx.x (x.x)	xx.x (x.x)	xx.x (x.x)	xx.x (x.x)	xx.x (x.x)
Transfer Factor (TLCO (as a percentage of the predicted value (%))	xx.x (x.x)	xx.x (x.x)	xx.x (x.x)	xx.x (x.x)	xx.x (x.x)	xx.x (x.x)
Sputum Sample						
Quantitative PCR Titre(copies)	xx.x (x.x)	xx.x (x.x)	xx.x (x.x)	xx.x (x.x)	xx.x (x.x)	xx.x (x.x)
Presence of EBV	Yes	n (x.x%)				
	No	n (x.x%)				

**Table x.x Secondary Outcomes(Lung Function)**

	Valaciclovir	Placebo	Difference (95% CI)	P-Value
Change in Forced Expiratory Volume (FEV1 (L)) from baseline to week 8	xx.x (x.x)	xx.x (x.x)	xx.x (xx.x – xx.x)	0.xx
Change in Forced Expiratory Volume in 1 second (FEV1 as a percentage of the predicted FEV1 value (%)) from baseline to week 8	xx.x (x.x)	xx.x (x.x)	xx.x (xx.x – xx.x)	0.xx
Change in Forced Vital Capacity (FVC (L)) from baseline to week 8	xx.x (x.x)	xx.x (x.x)	xx.x (xx.x – xx.x)	0.xx
Change in Mid Expiratory Flow (MMEF 25-75% (L/s)) from baseline to week 8	xx.x (x.x)	xx.x (x.x)	xx.x (xx.x – xx.x)	0.xx
Change in Peak Expiratory Flow(PEF (L/s)) from baseline to week 8	xx.x (x.x)	xx.x (x.x)	xx.x (xx.x – xx.x)	0.xx
Change in FEV1/FVC Ratio (%) from baseline to week 8	xx.x (x.x)	xx.x (x.x)	xx.x (xx.x – xx.x)	0.xx
Change in Transfer Factor (TLCO (as a percentage of the predicted value) (%)) from baseline to week 8	xx.x (x.x)	xx.x (x.x)	xx.x (xx.x – xx.x)	0.xx

**Table x.x Lung Function Exploratory Subgroups**

	EBV Suppression	Valaciclovir N = <n>	Placebo N = <n>	Difference (99% CI)	Interaction Term*
Change in Forced Expiratory Volume (FEV1 (L)) from baseline to week 8	Yes	xx.x (x.x)	xx.x (x.x)	xx.x (xx.x – xx.x)	0.xx
	No	xx.x (x.x)	xx.x (x.x)	xx.x (xx.x – xx.x)	
Change in Forced Expiratory Volume in 1 second (FEV1 as a percentage of the predicted FEV1 value (%)) from baseline to week 8	Yes	xx.x (x.x)	xx.x (x.x)	xx.x (xx.x – xx.x)	0.xx
	No	xx.x (x.x)	xx.x (x.x)	xx.x (xx.x – xx.x)	
Change in Forced Vital Capacity (FVC (L)) from baseline to week 8	Yes	xx.x (x.x)	xx.x (x.x)	xx.x (xx.x – xx.x)	0.xx
	No	xx.x (x.x)	xx.x (x.x)	xx.x (xx.x – xx.x)	
Change in Mid Expiratory Flow (MMEF 25-75% (L/s)) from baseline to week 8	Yes	xx.x (x.x)	xx.x (x.x)	xx.x (xx.x – xx.x)	0.xx
	No	xx.x (x.x)	xx.x (x.x)	xx.x (xx.x – xx.x)	
Change in Peak Expiratory Flow (PEF (L/s)) from baseline to week 8	Yes	xx.x (x.x)	xx.x (x.x)	xx.x (xx.x – xx.x)	0.xx
	No	xx.x (x.x)	xx.x (x.x)	xx.x (xx.x – xx.x)	
Change in FEV1/FVC Ratio (%) from baseline to week 8	Yes	xx.x (x.x)	xx.x (x.x)	xx.x (xx.x – xx.x)	0.xx
	No	xx.x (x.x)	xx.x (x.x)	xx.x (xx.x – xx.x)	
Change in Transfer Factor (TLCO (as a percentage of the predicted value) (%)) from baseline to week 8	Yes	xx.x (x.x)	xx.x (x.x)	xx.x (xx.x – xx.x)	0.xx
	No	xx.x (x.x)	xx.x (x.x)	xx.x (xx.x – xx.x)	

\*Interaction term from ancova

**Table x.x Secondary Outcomes(Participant Compliance)**

	Valaciclovir	Placebo	Difference (95% CI)	P-Value
Overall Compliance	xx.x (x.x)	xx.x (x.x)	xx.x (xx.x – xx.x)	0.xx

